11.3. Statistical Analyses

This section presents a summary of the planned statistical analyses. A statistical analysis plan (SAP) that describes the details of the analyses to be conducted will be written before database lock.

Unless otherwise indicated, all testing of statistical significance will be 2-sided, and a difference resulting in a P value of ≤ 0.05 will be considered statistically significant. All other P values from key secondary endpoints, after a non-significant P value is reached as well as other additional endpoints, will be considered exploratory.

Summary statistics will be provided for the variables described in the following subsections. Continuous variable summaries will include the number of patients, mean, standard deviation (SD), first quartile, median, third quartile, minimum, and maximum. Categorical variables will include the frequency and percentage of patients in each category.

11.3.1. Study Patients and Demographics

11.3.1.1. Disposition and Withdrawals

The numbers of patients screened, failed screening, randomized, receiving Injection 1 or 2, completing, and withdrawing, along with reasons for withdrawal and timing of withdrawal, will be tabulated overall and by treatment group. Reasons for not receiving Injection 2 will also be tabulated. The number of patients in each analysis population will be reported.

11.3.1.2. Protocol Deviations

Protocol deviations will be identified and important deviations will be classified before unblinding and will be summarized or listed as appropriate. Important protocol deviations affecting primary efficacy evaluation will be used to assess patient inclusion into PP and mPP populations.

11.3.1.3. Demographics and Other Baseline Characteristics

These analyses will be conducted for all analysis populations.

Demographic variables will include age, sex, race, weight, BMI, and region. Baseline patient characteristics will include medical history, including confirmation of OA diagnosis and time since diagnosis, Kellgren-Lawrence Grade, normalized WOMAC scores, and average daily pain.

11.3.2. Exposure and Compliance

All patients will receive up to 2 study drug injections at the study site under the surveillance of appropriate study personnel and, therefore, no compliance will be calculated. Injection procedure details and study drug batch or lot number(s) will be recorded in the patient's EDC system and summarized or listed as appropriate.

11.3.3. Efficacy Analysis

Efficacy variables will be summarized by treatment group and by injection period within each group using the FAS population, unless otherwise specified. For all the continuous variables, the normalized numbers will be used for analysis, where applicable, unless otherwise specified.

The overall type I error rate will be controlled for primary and key secondary endpoints using hierarchical testing, based on a fixed-sequence procedure.

[figure not shown]
If statistical significance is declared for the primary analysis, formal statistical inference will continue at the 0.05 level for the secondary endpoints in the defined sequence until a non-significant result is reached. All other P values from key secondary endpoints, after a non-significant P value is reached, as well as other additional endpoints, will be considered exploratory.

11.3.3.1. Primary Analysis

The primary efficacy analysis and estimation of the primary estimand will be based on the FAS population, the mPP population, and the PP population.

The primary estimand is the difference in mean change from Baseline in WOMAC Pain score at Week 12 between TLC599 vs. Placebo (as defined in the Treatment Assignment Table in Section 7.2). The endpoint and intercurrent events for the primary estimand are defined as follows:

- Endpoint: Change from Baseline in WOMAC Pain score at Week 12
- Intercurrent Events:

An ANCOVA will be performed with treatment group as a fixed effect and Baseline WOMAC Pain score as a covariate. Multiple imputation will be used to impute missing intermittent and post-withdrawal WOMAC Pain scores considered to be missing at random. Post-withdrawal missing data due to lack of efficacy, AE, or surgical procedure/IA drug administration in the index knee will be assumed to be MNAR; all other missing and post-withdrawal data will be assumed to be MAR.

The ANCOVA model will be conducted on each imputation and the results will be combined using Rubin's rules in SAS PROC MIANALYZE.

The least-squares mean comparing TLC599 to Placebo along with the corresponding 95% confidence interval, will be used to estimate the treatment difference.

Sensitivity analyses will be conducted to estimate sensitivity estimators and to assess the robustness of efficacy results, including:

- A sensitivity analysis using a tipping point procedure to assess the robustness of the multiple imputation results.
- A mixed-effects model repeated measures (MMRM) approach will be used as a sensitivity analysis for the primary endpoint. Treatment group, study visit (as a categorical variable) and

site will be modeled as fixed effects, with a treatment-by-visit interaction and baseline WOMAC Pain score as a covariate. Patient will be included as a random effect. Prior to implementing the model, MNAR data due to intercurrent events will be imputed using BOCF and non-missing data affected by the use of intercurrent medications and procedures will be replaced using BOCF, as described for the primary analysis method. The MMRM will include both observed and BOCF imputed data.

If further sensitivity analysis on the primary endpoint is performed, it will be described in the SAP. Descriptive summaries (such as mean, standard error, first quartile, median, third quartile, minimum, and maximum) will also be provided for the primary endpoint.

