The overall type I error rate will be controlled for primary and key secondary endpoints using hierarchical testing based on a fixed-sequence procedure. If statistical significance is declared for the primary analysis, formal statistical inference will continue at the 0.05 level for the secondary endpoints in the defined sequence until a non-significant result is reached. All other P values from key secondary endpoints, after a non-significant P value is reached, as well as other additional endpoints, will be considered exploratory.

An analysis of covariance (ANCOVA) model with treatment group as fixed effect and baseline value of the endpoint (when applicable) as covariates will be performed for the primary and key secondary continuous endpoints.

Sensitivity analyses will be conducted to estimate sensitivity estimators and to assess the robustness of efficacy results.

Additional Endpoints:

Additional endpoints and subgroup analyses will also be tested at a 2-sided 0.05 significance level.

The analysis of all continuous and categorical additional endpoints will be performed using an ANCOVA model

Safety Analysis:

Safety variables include physical examination, vital signs assessments (heart rate, respiratory rate, sitting blood pressure, and temperature), clinical laboratory assessments (hematology, chemistry, urinalysis), HbA1c, morning serum cortisol, [REDACTED] 12-lead electrocardiogram (ECG), knee radiographs, concomitant medications/therapies, AEs, and signs and symptoms of adrenal insufficiency. Medical history and AEs will be coded using the Medical Dictionary for Regulatory Activities (MedDRA), and concomitant medication will be coded using the World Health Organization Drug (WHODrug) Global Dictionary. Continuous safety data will be summarized by visit and include changes from baseline. Continuous data will also be converted to categorical values where possible (i.e., below, within, and above normal ranges) and summarized in shift from baseline tables. Categorical safety data collected by visit will be summarized showing the counts and percentages in each category at each visit, as well as shifts from baseline as appropriate.

Interim Analysis:

An interim analysis will not be performed.

SAMPLE SIZE DETERMINATION

This is a 3-arm parallel-group randomized controlled study. Approximately 500 patients will be randomized in

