7.6. Method of Assigning Patients to Treatment Groups

In this parallel-group randomized study, patients who meet study eligibility criteria will be randomly assigned in a 2:1:1 ratio to 12 mg TLC599, 4 mg DSP, or Placebo (normal saline). The randomization schedule will be computer generated using a permuted block algorithm and will randomly allocate study drug to randomization numbers. The randomization numbers will be assigned sequentially through a central interactive web response system (IWRS) as patients meet the eligibility criteria. Study center will not be a blocking factor in the randomization schedule.

The randomization schedule will be prepared by [REDACTED] before the start of the study. No one involved in the study performance will have access to the randomization schedule before official unblinding of treatment assignment. No patient will be randomized into this study more than once.

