11.3.3.3. Exploratory Analyses

For additional endpoints derived using the baseline prior to Injection 1, descriptive statistics for each variable will be presented for each visit until the end of study and summarized by treatment group and by injection period within each group. For additional endpoints derived using the baseline prior to Injection 2, descriptive statistics for each variable will be presented by treatment group. Efficacy endpoints relative to Injection 2 baseline will only be analyzed for patients who receive Injection 2.

The analysis of all continuous additional endpoints will be performed using an ANCOVA model as described for the single-dose primary endpoint.

Categorical exploratory endpoints will be analyzed using the same methodology as the categorical secondary endpoints.

P values from additional endpoints will be considered nominal and no adjustments for multiplicity will be made.

Subgroup analyses of the primary and secondary endpoints will be performed by age (<65 or \geq 65 years), sex, race (Caucasian or non-Caucasian), and Kellgren-Lawrence grade (2 or 3). Further details will be provided in the SAP.

Mean value, mean change, and percent change from baseline in WOMAC Pain and weekly average daily pain will be plotted over time.

A cumulative distribution plot of percent change in WOMAC Pain by treatment group will be produced for each time point from Injection 1 Baseline through Week 52. Patients who discontinue treatment are defined as non-responders with 0% improvement (no change from Baseline).

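### The primary ANCOVA is valid but adjusts only for baseline WOMAC Pain; pre-specifying screening daily NRS and Kellgren-Lawrence grade could add modest, assumption-dependent precision

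*Combined protocol and SAP*

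**What the plan says.** The primary model in Section 11.3.3.1 is stated in one sentence: "An ANCOVA will be performed with treatment group as a fixed effect and Baseline WOMAC Pain score as a covariate". The Protocol Summary gives the same rule for the primary and key secondary continuous endpoints: "treatment group as fixed effect and baseline value of the endpoint (when applicable) as covariates". Section 11.3.3.2 carries the primary method over to the continuous secondary endpoints.

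Other baseline data are collected. Section 11.3.1.3 lists "Kellgren-Lawrence Grade, normalized WOMAC scores, and average daily pain" among the baseline characteristics, and adds: "Demographic variables will include age, sex, race, weight, BMI, and region". Two of these are also entry requirements in Section 6.6.1. The daily index-knee NRS must average between 5.0 and 9.0, from diary entries on five or more of the seven days before randomization. The K-L grade must be 2 or 3 on central reading.

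K-L grade appears again in Section 11.3.3.3, but only as a subgroup factor. Site enters only the MMRM sensitivity model, where "site will be modeled as fixed effects, with a treatment-by-visit interaction and baseline WOMAC Pain score as a covariate". Section 7.6 states: "Study center will not be a blocking factor in the randomization schedule". It names no stratification factor.

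**The concern.** Baseline WOMAC Pain is a single-visit score with a 24-hour recall. The diary NRS averages several days, so it may carry information on pain severity that one visit misses. K-L grade describes structural severity, which neither pain score measures. If either predicts Week 12 WOMAC Pain beyond the baseline score, the present model leaves explainable variance in the standard error.

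This would affect more than the primary test. Section 11.3.3 uses a fixed sequence, and Section 11.1.1.2 places 12 key secondary tests behind the primary. The first non-significant result ends formal inference, so a small gain in precision is useful at each continuous step. With no named stratification factor, chance imbalance in diary pain or K-L grade is handled neither by the design nor by the primary model.

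**Working it through.** **The plan's own figure.** Section 11.4 gives about 500 patients, 2:1:1, which is 250, 125 and 125. The assumptions behind this number are not readable, so it cannot be reproduced, and that is not counted against the plan. For orientation, 250 against 125 at two-sided 0.05 with no dropout detects a standardized difference of (1.960 + 0.842) × √(1/125 + 1/250) = 0.307 at 80% power, and 0.355 at 90%. The true starting power is unknown, so both 80% and 90% are used below.

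**Inputs.**
- A against C: 250 + 125 = 375 patients, on the assumption that the contrast is fitted on these two groups.
- Added covariates: mean daily NRS and K-L grade (2 vs 3), so p = 2.
- R² is the share of residual variance explained beyond baseline WOMAC Pain. It is an assumption and is varied.

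**Formulas.**
- Variance factor: V = (1 − R²) × 371/(371 − p) = (1 − R²) × 371/369.
- SE change: √V − 1.
- Power: Φ((1.960 + z)/√V − 1.960), with z = 0.842 for 80% and 1.282 for 90%.

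| Added R² | V | SE change | From 80% | From 90% |
|---|---|---|---|---|
| 0 | 1.0054 | +0.3% | 79.8% | 89.8% |
| 0.02 | 0.9853 | −0.7% | 80.6% | 90.4% |
| 0.05 | 0.9552 | −2.3% | 81.8% | 91.3% |
| 0.10 | 0.9049 | −4.9% | 83.8% | 92.6% |

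Break-even, where V = 1: R² = 1 − 369/371 = 0.5%.

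**Check of the method.** 3,000 simulated trials per setting (250 vs 125, five added covariates, start near 90%) gave power moving from 90.0% to 89.2% at R² = 0, from 89.0% to 90.6% at 0.05, and from 90.1% to 92.1% at 0.10. The formula with p = 5 gives 89.6%, 91.0% and 92.4%. Type I error was 5.0% to 5.4% for both models.

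**Which R² is plausible?** For NRS alone, let r1 be the correlation of baseline WOMAC Pain with outcome, r2 that of NRS with outcome, and r12 that between the two. Then added R² = [(r1² + r2² − 2·r1·r2·r12)/(1 − r12²) − r1²]/(1 − r1²). All three are assumptions: r1 of 0.3, 0.4 or 0.5; r2 of 0.2, 0.3 or 0.4; r12 of 0.5 or 0.7.
- Low example (0.4, 0.3, 0.7): (0.082/0.51 − 0.16)/0.84 = 0.0009.
- High example (0.3, 0.4, 0.5): (0.13/0.75 − 0.09)/0.91 = 0.092.
- Of the 18 combinations, 13 fall below 0.04, one equals 0.04, and four lie between 0.059 and 0.092.

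At R² = 0.04, V = 0.96 × 371/369 = 0.965, and power goes from 80% to 81.4% or from 90% to 91.0%. The documents give no basis for a figure for K-L grade.

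**The case against.** The strongest reply is that this is a matter of preference. The planned ANCOVA already includes the baseline value of the outcome, is unbiased under randomization, and omits no named stratification factor. A more heavily adjusted model, with site, is pre-specified as a sensitivity analysis. All of that stands.

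Four stronger readings are tempting, and the documents do not support them:
- **That the plan ignores known prognostic factors.** No section says that daily NRS or K-L grade predicts Week 12 WOMAC Pain beyond the baseline score. NRS measures nearly the same construct and is cut to 5.0–9.0 at entry; K-L grade is cut to 2 or 3.
- **That adjustment is free.** It costs degrees of freedom, and the protocol wording would have to change.
- **That the gain can be read as 500/(1 − R²), or 510, 526 or 556 patients.** This counts Group B, which is not in the primary contrast, and omits the degrees-of-freedom cost.
- **That PGIC is analysed with no covariate at all.** The Summary's phrase "baseline value of the endpoint (when applicable) as covariates" applies to continuous endpoints. For categorical secondaries, Section 11.3.3.2 compares predictive marginal proportions. That implies a fitted model, and its covariates are not readable. If PGIC is treated as continuous, the primary method applies. Neither route shows an unadjusted analysis.

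Section 11.3.3.1 also describes replacing some values by baseline observation carried forward. Those patients have zero change whatever their covariates, which can dilute the added R². The linear formula does not carry over directly to the responder endpoint or to a categorical PGIC.

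Missing covariate data are a weaker objection, because eligibility requires both values.

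**Conclusion.** The point holds as an optional gain in efficiency. The one-covariate model is certain from the text; the size of the gain is not. For an added R² of 2% to 10%, power rises by about 0.6 to 3.8 points from 80%, or 0.4 to 2.6 points from 90%. Range restriction and carry-forward make the lower end more likely, so about one point is a sensible expectation. The downside is bounded at about 0.2 points.

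These figures rest on an assumed R², an assumed starting power, complete data in 375 patients and a linear model. They do not show that the planned analysis is wrong or that the trial is underpowered.

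**What to change.** Before unblinding, revise Section 11.3.3.1 and the matching Summary text so that the primary ANCOVA contains treatment group, baseline WOMAC Pain, mean daily index-knee NRS over the last seven screening days, and K-L grade (2 vs 3). Put the same covariates in the multiple-imputation model, so that it is consistent with the analysis model, and in the continuous key secondary models. Keep the one-covariate ANCOVA as a supportive analysis. State a rule for any patient randomized without one of the two values.

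No new data are needed. The statistical cost is the small loss above if the covariates prove uninformative. The administrative cost is SAP text, which Section 11.3 says will be written before database lock, plus a formal protocol amendment. Section 12.8 requires sponsor approval, investigator signature and ethics approval for that amendment.

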6.7. Patient Withdrawal from the Study

All patients will be advised that they are free to withdraw from participation in this study at any time, for any reason, and without prejudice. The investigator should make every reasonable attempt to keep patients in the study; however, patients must be withdrawn from the study if they withdraw consent to participate. Patients who do not receive Injection 2 do not need to be withdrawn and will be encouraged to continue in the study through 52 weeks of follow-up. If a patient does not receive Injection 2, it will not be considered a protocol deviation. Investigators must attempt to contact patients who fail to attend scheduled visits by telephone or other means to assess the possibility of an AE being the cause of withdrawal. Should this be the cause, the AE must be documented, reported, and followed as described in Section 9.2.

A participant should be withdrawn from the study if any of the following occurs:

- Pregnancy
- Significant study non-compliance
- Lost to follow-up
- A surgical procedure or IA drug administration in the index knee
- Lack of therapeutic effect that is intolerable or otherwise unacceptable to the patient
- If any clinical AE, laboratory abnormality, or other medical condition or situation occurs such that continued participation in the study would not be in the best interest of the participant
- The investigator or the Sponsor stops the study for any reason

If important restricted medication deviations occur, they should be discussed with the medical monitor before withdrawing the patient from the study.

The investigator should contact the medical monitor to discuss any non-compliance or safety concerns before withdrawing a patient from the study.

The reason for participant withdrawal from the study will be recorded on the eCRF. Patients who sign the ICF, are randomized, and receive study drug, and subsequently withdraw, or are withdrawn from the study, will not be replaced.

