7.10. Prohibited Therapies

All concomitant medications used (including over-the-counter medications and herbal supplements) will be recorded in the source document and on the appropriate eCRF.

The following therapies are prohibited after the informed consent is signed, and throughout the study, unless otherwise specified:

- IA corticosteroid in any joint
- IA hyaluronic acid in any knee joint
- Systemic corticosteroids (topical use allowed except on the index knee)
- Acetaminophen within 24 hours prior to Baseline and subsequent study visits

- Non-steroidal anti-inflammatory drugs within 14 days before the Baseline visit and throughout the study (topical use allowed except on the index knee)
- New initiation of duloxetine, pregabalin and gabapentin (a patient may continue the prior use of these drugs during the study)
- Platelet-rich plasma or other prolotherapy
- Opioid use is not permitted, with the exception of hydrocodone, oxycodone, or tramadol, which may be used with the following limitations:
 - Any combination analgesic containing an opioid is prohibited
 - However, episodic use (<4 days per week) of hydrocodone, oxycodone, or tramadol is permitted
 - The use of any opioid (including hydrocodone, oxycodone, or tramadol) within 24 hours before the Baseline visit and subsequent study visits is prohibited
- Any chemotherapeutic or systemic immunosuppressant agents for inflammatory diseases
- Anti-coagulants, including warfarin, heparin, low molecular weight heparin, or dabigatran (low-dose acetylsalicylic acid and other anti-platelet medications allowed)
- Live attenuated vaccine
- Any investigational therapy
- Physical and occupational therapy or new rehabilitation program in index knee
- Acupuncture or any surgical or invasive procedure on either knee (including study knee joint synovial fluid aspiration except prior to study drug administration)
- Oral cannabidiol (CBD) in any form; inhalation is allowed and topical use is allowed except on the index knee

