Patients receiving excluded therapies during the screening period will be treated as screen failures and ineligible for randomization. If a patient uses any prohibited medication or treatments mentioned as above after study drug administration during the study period, it will be defined as a protocol deviation. Whether such protocol deviation is considered as significant study non-compliance leading to withdrawal will be based on the investigator's judgment after consulting the sponsor and the blinded medical monitor.

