11.2. Analysis Populations

The following analysis populations are planned for this study:

Safety Population (SAF): The Safety Population includes all patients who receive any dose of study drug; the population will be determined for each study period. Injection 1 Period reporting will require that Injection 1 has been received; Injection 2 Period reporting will require that Injection 2 has been received. The SAF population will be the primary population for safety evaluation.

Full Analysis Set (FAS): The FAS includes all randomized patients who receive Injection 1. The FAS population will be the primary population for efficacy analysis, as well as for descriptive summaries other than safety (demographic and baseline, disposition, protocol deviation, medical history, etc.).

Per Protocol Population (PP): The PP Population includes all patients who receive 2 doses of study drug, have primary efficacy evaluation at Weeks 12, 24, and 36, and do not have important protocol deviations affecting primary efficacy evaluation.

Modified Per Protocol (mPP): The mPP Population includes all patients who receive the first dose of study drug, have primary efficacy evaluation at Weeks 12 and 24, and do not have important protocol deviations affecting primary efficacy evaluation.

The **PP** and **mPP** populations will be used for supportive analysis of selected efficacy endpoints. For the PP population, patients must have a valid WOMAC Pain assessment at Baseline, Week 12, Week 24, and Week 36; for the mPP population, patients must have a valid WOMAC Pain assessment at Baseline, Week 12, and Week 24. (A valid assessment is within the analysis visit window and not excluded due to an intercurrent event as described in Section 11.3.3.1).

Important protocol deviations are determined in accordance with the protocol deviation guidance plan. Membership in the PP and mPP analysis populations will be determined after blinded data review of important protocol deviations affecting primary efficacy evaluation before database lock and study unblinding.

If a patient is randomized incorrectly or is administered the incorrect study drug, analyses of the FAS population will be based on the assigned treatment, whereas analyses of all other populations will be based on the actual treatment received.

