11.3.3.2. Secondary Analyses

Continuous secondary endpoints will be analyzed using the same methodology as for the primary endpoint, unless otherwise indicated.

For analysis of categorical secondary endpoints, the difference in the predictive marginal proportions will be the basis of comparison between treatment groups.

The corresponding 95% CI and P value will also be presented.

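### Does Section 11.3.3.1 treat the same prohibited-drug use in two ways, as zero change if the patient stays and as MAR if the patient is withdrawn for it?

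*Combined protocol and SAP*

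**What the plan says.** Four parts of the plan bear on this.

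- **Missing scores (Section 11.3.3.1).** "Post-withdrawal missing data due to lack of efficacy, AE, or surgical procedure/IA drug administration in the index knee will be assumed to be MNAR". The next clause is the catch-all: "all other missing and post-withdrawal data will be assumed to be MAR". MAR scores are multiply imputed. MNAR data due to intercurrent events are set to BOCF; the visible text says this in the MMRM bullet.
- **Observed scores (Section 11.3.3.1, MMRM bullet).** "non-missing data affected by the use of intercurrent medications and procedures will be replaced using BOCF, as described for the primary analysis method". The closing reference shows that the same replacement belongs to the primary analysis. Section 11.2 agrees: a valid assessment is one "not excluded due to an intercurrent event as described in Section 11.3.3.1".
- **Withdrawal (Sections 6.7 and 7.10).** Prohibited-drug use after dosing is a protocol deviation. "Whether such protocol deviation is considered as significant study non-compliance leading to withdrawal" is left to the investigator, after consulting the sponsor and the blinded medical monitor. Section 6.7 adds: "If important restricted medication deviations occur, they should be discussed with the medical monitor before withdrawing the patient from the study". It lists significant non-compliance separately from lack of effect, AEs, and surgery or IA drug in the index knee.
- **Reach (Section 11.3.3.2).** "Continuous secondary endpoints will be analyzed using the same methodology as for the primary endpoint", unless otherwise indicated.

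The entries under the intercurrent-events bullet of Section 11.3.3.1 are not shown in the public text.

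**The concern.** Take two patients who use the same prohibited drug, for example a systemic corticosteroid. One stays in the trial, and if the score counts as affected it is set to baseline, a change of zero. The other is withdrawn for non-compliance over that use. This reason is not among those named as MNAR, so the catch-all makes the missing score MAR, and multiple imputation gives the patient a change like that of comparable patients in the trial.

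The value given to one intercurrent event would then depend on a discretionary withdrawal decision and the reason recorded for it. At stake are a uniquely defined primary estimand, some movement in the TLC599-Placebo difference, and the same ambiguity in the continuous secondary endpoints.

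**Working it through.** **Step 1: trace the visible rules**

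| Situation | Handling |
|---|---|
| Stays in; score affected by an intercurrent medication | BOCF |
| Withdrawn; reason recorded as lack of efficacy or AE | MNAR, BOCF |
| Withdrawn for surgery or IA drug in the index knee | MNAR, BOCF |
| Withdrawn for non-compliance over another drug | Catch-all: MAR, multiple imputation |

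Only the last row can conflict with the first.

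**Step 2: what the withheld list would have to say.** A conflict at Week 12 needs three things.

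1. The drug counts as an intercurrent medication. The visible BOCF trigger is intercurrent medication, not prohibited medication. Section 7.10 also prohibits live vaccines and anticoagulants, so the two sets need not match.
2. The list does not already deal with scores missing after withdrawal. The catch-all has no visible exception. However, the MMRM bullet speaks of MNAR data due to intercurrent events, which ties MNAR status to that list.
3. The use would still make the Week 12 score count as affected. If a drug taken at Week 4 affects scores for only a short time, a patient who stays contributes the observed Week 12 score. MAR imputation is then the closer match for the patient who left, and BOCF would create the inconsistency.

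None of the three can be checked.

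**Step 3: size.** The documents give no rates, means or SD, so these are assumptions.

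- Mean Week 12 change: mA = -1.1 (TLC599), mC = -0.8 (Placebo), on the 0-4 scale.
- pA, pC: share of each arm withdrawn in this way before Week 12, 2% to 5%.
- k: share of the completer mean that MAR imputation credits, from 1 down to 0.2.
- f: share of these patients whose Week 12 score would have counted as affected, taken as equal in both arms.

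Shift in A-C, current rule minus BOCF for the affected patients:

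shift = k × f × (pA × mA - pC × mC)

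With k = f = 1, the comparator is BOCF for all such patients: (1 - pA) × mA - (1 - pC) × mC.

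| pA / pC | Shift | BOCF difference | Relative |
|---|---|---|---|
| 2% / 2% | -0.022 + 0.016 = -0.006 | -0.294 | 2.0% larger |
| 5% / 5% | -0.055 + 0.040 = -0.015 | -0.285 | 5.3% larger |
| 5% / 3% | -0.055 + 0.024 = -0.031 | -0.269 | 11.5% larger |
| 5% / 2% | -0.055 + 0.016 = -0.039 | -0.261 | 14.9% larger |
| 2% / 4% | -0.022 + 0.032 = +0.010 | -0.310 | 3.2% smaller |
| 2% / 5% | -0.022 + 0.040 = +0.018 | -0.318 | 5.7% smaller |

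The sign turns at pC/pA = 1.1/0.8 = 1.375. At k = 0.2 every shift is one fifth of the figure shown. At f = 0 it is zero. With assumed means of -1.2 and -0.9, the 5% / 2% case gives -0.060 + 0.018 = -0.042.

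**Step 4: scale.** 500 patients at 2:1:1 give 250 and 125. With an assumed SD of 0.8, SE = 0.8 × √(1/250 + 1/125) = 0.8 × 0.1095 = 0.088. The largest shifts are 0.039/0.088 = 0.44 and 0.042/0.088 = 0.48 of a standard error.

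**Step 5: test size.** Simulation used within-arm multiple imputation, 250 against 125 patients and between-visit correlation of 0.5 or 0.8. With no effect and equal use (2%/2% and 5%/5%, 3,200 runs in total), rejection was 4.7% under the MAR rule and 4.8% under BOCF for all users. The simulated settings gave shifts of -0.033 to +0.011, with standard errors of 0.088 to 0.090.

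**The case for a change.** The best argument for a change is about definition, not size. Under the estimand, one event should have one handling. The plan already follows that principle for index-knee procedures and IA drugs, where withdrawal for the event is MNAR and matches BOCF of observed scores. No parallel clause is visible for other drugs. If the withheld list does contain one, the unqualified catch-all contradicts it. The tipping point analysis tests the imputed values but does not say which rule applies. A sentence or two would settle the matter, using records already collected.

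The literal reading stands, and so does the point about the tipping point. The rest is weaker.

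- An added sentence would have to borrow the withheld definition and window. It might repeat what is already there or change no result.
- Section 11.3 calls itself a summary and leaves the detail to a SAP due before database lock. Assigning withdrawal reasons to imputation classes is ordinary work for that document, done blind.
- The group is narrow: prohibited use, then a discretionary withdrawal before Week 12, not recorded as lack of efficacy or AE. Section 6.7 asks investigators to try to keep patients in. The decision is made by a blinded investigator with a blinded monitor, although use itself could still differ between arms.
- Replacing an observed score and assuming a mechanism for an unobserved one are different operations. BOCF for both is one way to align them, not the only one.

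**Conclusion.** No change is called for. The visible text leaves a gap at one narrow point: data missing after withdrawal for non-compliance over an intercurrent medication. Whether it is a gap in the full plan depends on a list that is withheld, and withheld text cannot be counted as missing. An analyst who holds the full text can assign these few patients when the SAP details are written, check that the intercurrent-event definition and the catch-all agree, and use the same handling in the MMRM and the continuous secondary endpoints.

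Under the assumed means and 2% to 5% per arm, the choice moves the primary difference by -0.039 to +0.018 (up to 0.042 in size with the alternative means), less than half a standard error. These figures assume that every such patient would have counted as affected at Week 12 and that MAR credits the full completer mean, so smaller shifts are more likely. The direction depends on which arm has more such withdrawals. No type I error inflation was seen with no effect and equal use. The conclusion would need another look if blinded data showed withdrawals of this kind well above 5% per arm.
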